Sample size was calculated using data from previous studies that examined changes in FEV₁ in people with EIB. Two studies by Anderson et al., in 2001 used a similar crossover design and found a detectable difference of 12% reduction in FEV₁ with a standard deviation of 14%. Calculation for a crossover design based on analysis of variance F-tests using these values with a power of 0.8 and an alpha level of 0.05 led to a sample size of 24 subjects. Previous data from FeNO in an asthmatic population were considered to make sure this sample size would be appropriate for FeNO measurement. Changes in FeNO measurements biased on a study by Niu et al., in 2018 showed a larger effect size than FEV₁ so the sample size based on FEV₁ measurement is more conservative.

Measures/Instruments

The two independent variables in this study are ozone pollution status and medication (salbutamol) status. Both independent variables will have a nominal level of measurement with two levels. The two levels of ozone air pollution are: 170 ppb ozone and room air. Room air in the lab where data collection will be done has low levels of ozone (typically less than 10 ppb) and other pollutants. While wearing nose clips, participants will be exercising on a stationary bike breathing in air from a mouthpiece that is connected to a sealed chamber. The sealed chamber will contain an ACT-5000 ozone generator (ACT-series, 2021). The ozone generator will either be turned on or off depending on the allocated treatment. The concentration of ozone will be

confirmed using an electrochemical ozone sensor that will be set up in the chamber. Electrochemical ozone sensors have been validated using linear association models that have reported R^2 values of 0.98 (Afshar-Mohajer et al., 2018). For the salbutamol condition, participants will take two puffs from a meter dose inhalers (MDI) designed to deliver 100 μg of salbutamol per puff or a trainer MDI for the placebo condition. To ensure reliability of the dose delivered participants will be told standardized instruction for using an MDI. Adhering to these instructions increases the consistency of the dose delivered (Sanchis et al., 2013). In addition, an aerochamber will be attached to the MDI which further increases dose consistency (Newman, 2004). Medication status will have two levels: 200 μg of salbutamol and placebo salbutamol.

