Rating of symptoms (dyspnea, cough, sore throat, headache, chest pain, and chest tightness) and blood pressure will also be measured. The selected symptoms were chosen because they have been recognized or are related to symptoms of ozone exposure (Lippmann, 1989). Dyspnea will be measured subjectively using a modified Borg scale that has previously been used to measure dyspnea and validated against other dyspnea measures (Gaber et al., 2019). The other symptoms will be subjective rated on a scale from 0-5. Blood pressure will be measured using an automated sphygmomanometer. In accordance with Hypertension Canada's guidelines on blood pressure measurement, blood pressure will be measured three times and the first measure will be thrown away while the latter two are averaged (Nerenberg et al., 2018).

Study Design

This research design can be characterized as a placebo-controlled crossover design with pre-post measures. There are two independent variables: ozone pollution status and medication status. The two levels of ozone pollution status are 170 ppb ozone and room air. The two levels of medication status are 200 µg of salbutamol and placebo medication. Participants will perform 30 minutes of submaximal exercise at 60% of their $VO_{2\max}$ in all four conditions. These conditions are salbutamol + ozone, placebo + ozone, salbutamol + room air, and placebo + room air. The order of the conditions on the experimental days will be randomized to one of four sequences. The four conditions will be labelled A (ozone + inhaler A), B (ozone + inhaler B), C (room air + inhaler A), and D (room air + inhaler B). The researchers will not know which inhaler (A or B) is placebo

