and which is salbutamol to facilitate blinding. The four condition sequences will be ABCD, BDAC, CABD, DCBA. These sequences represent a Latin Square crossover design, which is uniform both within periods and within sequences. In other words, each condition appears only once in each sequence and only once at a particular spot within the four sequences. This means that the sequences are balanced with respect to first order carry over effects because each condition precedes every other condition only once. For example, condition D is first only once and is preceded by condition A, B, and C only once. FeNO, spirometry, blood pressure, and symptom measures will be obtained before and immediately after, 30 minutes after, and 1 hour after exercise in each condition. Pre and post measures will be compared from the four conditions to examine how exercising in different combinations of ozone pollution and medication influence pulmonary function (spirometry) and inflammation (FeNO). The medication condition will be double blinded to control for the placebo effect and expectancy bias of the research. This will be done by having a placebo inhaler and a salbutamol inhaler labeled A and B by someone who is not collecting data. That way neither the participant nor the researcher collecting data will know whether placebo or real salbutamol is being used in a particular condition. The ozone condition will also be double blinded. This will be done by having the participant breathe air from a tube connected to a sealed chamber, which they will not be able to see inside, that has an ozone generator that is controlled on the opposite side of the chamber. A separate researcher will be controlling the ozone chamber and on room air will pretend to operate the generator for the room air conditions and actually operate the generator for the ozone conditions. Ozone levels will be recorded for all conditions and revealed to the main researcher after data collection is completed.

Procedures

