in subsequent trials at 60% of $VO_{2\max}$. A graded exercise test with a ramp protocol will be performed while expired gas is analyzed using a metabolic cart to measure $VO_{2\max}$ (Beltz et al., 2016). Participants will conduct a self-selected warm-up. Following the warm up, participants will start the exercise test at 75 or 100 Watts, with the workload increasing in a step-wise fashion by 10 or 20 Watts every two minutes until they feel that they can no longer continue or until they can no longer maintain a cadence of 60 rotations per minute (rpm). $VO_{2\max}$ will be considered achieved if three of the following four criteria are met: heart rate (HR) $>90\%$ of age-predicted maximum, respiratory exchange ratio >1.15 , plateau of oxygen consumption per minute (VO_2) with increasing work load, and volitional exhaustion (Beltz et al., 2016). Age-predicted maximum heart rate will be calculated as $220 - \text{age (years)}$.

Participants will return to the lab on four separate occasions to complete the four exercise trials in a random order. During each visit, participants will take two puffs from an MDI, wait 15 minutes, and then pre-exercise measures will be taken. Pre-exercise FeNO, blood pressure, and symptoms will be measured and then participants will put on a headset that includes a mouth piece that will be used for spirometry and will control inspired air during exercise. Pre-exercise spirometry will be measured and then participants will perform a self-selected warm-up. Once they are ready, participants will exercise at a resistance that will elicit 60% of their $VO_{2\max}$ for 30 minutes while breathing through a one-way valve connected to a sealed chamber. The chamber will either contain room air or 170 ppb ozone being generated by an ozone generator. After 5 minutes and 25 minutes of exercise participants will do an IC. After 30 minutes are complete, post-exercise blood pressure, symptoms, spirometry and FeNO will be measured. All visits will be separated by 48 hours to prevent carryover effects from previous exposure to ozone or salbutamol.

This 48-hour duration was chosen because it is longer than five half-lives of salbutamol medication.

Ethical Considerations

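### The four listed sequences lack the period and first-order carryover balance the plan claims; replacing CABD with CADB restores it

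*Combined protocol and SAP*

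**What the plan says.** The Study Design section describes a "placebo-controlled crossover design with pre-post measures" with four conditions: A (ozone, inhaler A), B (ozone, inhaler B), C (room air, inhaler A) and D (room air, inhaler B). Participants are randomised to one of four orders: "The four condition sequences will be ABCD, BDAC, CABD, DCBA".

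Three properties are then claimed for this list:

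- Uniformity: "each condition appears only once in each sequence and only once at a particular spot within the four sequences".
- Carryover balance: "the sequences are balanced with respect to first order carry over effects because each condition precedes every other condition only once".
- A worked example: "condition D is first only once and is preceded by condition A, B, and C only once".

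On washout, the Procedures section says: "All visits will be separated by 48 hours to prevent carryover effects from previous exposure to ozone or salbutamol". The reason given is: "This 48-hour duration was chosen because it is longer than five half-lives of salbutamol medication".

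**The concern.** The list and its description disagree within one paragraph. Each condition does occur once per sequence, but the other claimed properties can be counted by hand and fail.

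The hypothesis concerns salbutamol against placebo before exercise in ozone, which is A versus B (which inhaler is active is masked). If the orders are unbalanced, this contrast can absorb a trend over visits or a residual effect of an ozone exposure 48 hours earlier. The washout is said to cover ozone, but its rationale rests only on the half-life of salbutamol. For ozone, sequence balance is the only safeguard for which the text gives a reason. The documents name no period or carryover terms that would compensate, and an analyst who trusts the claim could leave them out.

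**Working it through.** **Inputs.** The sequences and condition labels come from Study Design. The sample size (24), the 12% FEV1 difference and the SD ("with a standard deviation of 14" per cent) come from the end of Sample and Recruitment. Assumed: 6 participants per sequence, because no allocation ratio is stated. The documents give no visit drift t and no ozone carryover k, so both stay symbolic, in units of the outcome analysed.

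**1. Claimed balance.** The claim requires all 16 condition-by-visit counts and all 12 ordered adjacent pairs to equal 1.

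| | Visit 1 | Visit 2 | Visit 3 | Visit 4 |
|---|---|---|---|---|
| Printed list | A, B, C, D | B, D, A, C | C, A, B, B | D, C, D, A |
| With CADB | A, B, C, D | B, D, A, C | C, A, D, B | D, C, B, A |

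In the printed list, AB and BD occur twice, AD and DB never, and the other eight pairs once. D is preceded by B twice, C once and A never, so the plan's own example is false. With CADB, every count is 1 and the example is true. Among all 24 possible third sequences, with the other three fixed, only CADB gives position balance and only CADB gives carryover balance. Changing any other single sequence does not restore both.

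**2. Unadjusted bias in A−B.**

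- Mean position: A (1+3+2+4)/4 = 2.50; B (2+1+3+3)/4 = 2.25. Drift bias is (2.50 − 2.25)t = +0.25t.
- Directly after an ozone visit: A in 1 of 4 sequences, B in 2 of 4. Carryover bias is (1/4 − 2/4)k = −0.25k.
- Any earlier ozone visit: 2 of 4 for each, so equal.

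For the inhaler-by-ozone interaction, (A−B)−(C−D), mean positions for C and D are 2.50 and 2.75, and each follows an ozone visit in 2 of 4 sequences. The biases are [0.25 − (−0.25)]t = +0.50t and (−0.25 − 0)k = −0.25k.

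**3. With participant and period terms.** The least-squares estimate of A−B is the average over the four sequences of these weighted sums († marks a visit directly after ozone):

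| Sequence | Visit 1 | Visit 2 | Visit 3 | Visit 4 |
|---|---|---|---|---|
| ABCD | 1 | −7/6 † | 1/3 † | −1/6 |
| BDAC | −7/6 | 1/6 † | 4/3 | −1/3 † |
| CABD | 0 | 1 | −5/6 † | −1/6 † |
| DCBA | 1/6 | 0 | −5/6 | 2/3 † |

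Rows and columns sum to zero, so participant and visit effects cancel. The † weights sum to (−7+2+1−2−5−1+4)/6 = −4/3, and −4/3 ÷ 4 gives −0.33k. The interaction bias with period terms is −0.42k. Adding an indicator for a preceding ozone visit removes the A−B carryover bias. With CADB and equal allocation, all these biases are zero.

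For an assumed k of 0 to 6 FEV1 percentage points, the A−B bias with period terms alone is 0 to 6/3 = 2.0 points, against the planned 12.

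**4. Precision and power.** Var(A−B) = v·s²/24, where s is the within-person SD. Power uses the noncentral t, two-sided 0.05, with noncentrality 12/(s√(v/24)). Example with period terms and s = 14: printed 12/(14√(2.167/24)) = 2.85, power 0.80; CADB 12/(14√(2/24)) = 2.97, power 0.83.

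| Model (participant plus) | v, printed / CADB | Power, 14% as within-person SD | Power, 14% as SD of difference |
|---|---|---|---|
| period (66 df) | 2.167 / 2.000 | 0.80 / 0.83 | 0.98 / 0.99 |
| period, preceding ozone (65 df) | 2.357 / 2.000 | 0.77 / 0.83 | 0.97 / 0.99 |
| period, four-level carryover (63 df) | 3.776 / 2.200 | 0.57 / 0.80 | 0.85 / 0.98 |

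The within-person reading agrees with the plan's own sample size: a paired t-test with SD of difference 14√2 has power 0.793 at 23 participants and 0.811 at 24. The reading remains an assumption. The documents give no FeNO SD, so these figures are for FEV1 only.

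**The case against.** The contradiction itself is not open to argument; its weight is.

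- The description fits the CADB square exactly, so the natural explanation is a two-letter slip in one string. The randomisation list is not in the documents. If it holds CADB, the whole consequence is a text correction. This stands, and it is why checking the list comes first.
- t and k are unknown, and the 0 to 6 range has no source in the text; its top is half the planned effect, still present 48 hours later. Applying the 12% to A−B is also a reading of the sample-size paragraph. The sizes are illustrations, not estimates.
- Measurements are taken before and after exercise at each visit. A shift that moves both equally cancels in a change score. This stands; bias needs drift or carryover in the outcome actually analysed.
- The power loss is small in simple models, and nil with participant terms only (v = 2.000 for both squares). The fall to 0.57 needs four-level carryover, which neither the plan nor the fix below requires. It should not drive the judgement.
- No allocation ratio is stated. Under simple randomisation to the CADB square, the A−B position differences are −1, 2, −2 and 1, so the chance imbalance in mean position has SD √(2.5/24) = 0.32 visits, larger than 0.25. But chance imbalance averages to zero over randomisations, whereas the printed error is systematic. Equal allocation removes it.

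**Conclusion.** The plan is wrong as written: the listed sequences have neither the period uniformity nor the first-order carryover balance claimed, and the worked example for D is false. These facts need no assumption.

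The consequence is conditional. If CABD is run with 6 participants per sequence, A−B carries a bias of +0.25t and −0.25k unadjusted, or 0 and −0.33k with period terms alone. Power falls from 0.83 to between 0.80 and 0.77 in the simpler adjusted models, reading 14% as a within-person SD; under the other reading the loss is one to two percentage points. A−B remains estimable. The point should be fixed because the claim concerns the main contrast and the repair is almost free, but it is not fatal to the trial.

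**What to change.** Check the randomisation list actually used, then take the matching course:

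- **The list already has CADB:** correct the text only.
- **The list has CABD and it has not been run:** replace it, giving ABCD, BDAC, CADB, DCBA. Allocate equally across sequences, fit participant and period terms, and add first-order carryover as a sensitivity term. The cost is two letters and a sentence of analysis wording, with no added visits or participants.
- **Participants have been run on CABD:** remove the balance claim. Before unblinding, specify period terms plus at least an indicator for a preceding ozone visit; period terms alone are not enough. Compared with period terms alone, the indicator raises the A−B variance by 2.357/2.167 − 1, about 9%, and lowers power from 0.80 to 0.77 under the within-person reading.

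### Two fixed inhaler letters and four printed sequences leave a route by which data collectors could deduce ozone status at exposures 2 to 4, and the blinding text does not close it

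*Combined protocol and SAP*

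**What the plan says.** Study Design defines the conditions as "A (ozone + inhaler A), B (ozone + inhaler B), C (room air + inhaler A"), with D being room air plus inhaler B. Each participant is randomised to one of four orders: "The four condition sequences will be ABCD, BDAC, CABD, DCBA".

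On the drug, the section says "The researchers will not know which inhaler (A or B) is placebo". This is achieved by "having a placebo inhaler and a salbutamol inhaler labeled A and B by someone who is not collecting data".

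On the exposure, it says "The ozone condition will also be double blinded". The means are a sealed chamber that the participant cannot see into, an operator ("A separate researcher will be controlling the ozone chamber") who mimics running the generator on room-air days, and delayed disclosure: "Ozone levels will be recorded for all conditions and revealed to the main researcher after data collection is completed".

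Procedures makes the first of five lab visits a screening day, so exposures 1 to 4 are lab visits 2 to 5. At each exposure visit the inhaler is taken first, and the pre-exercise measures follow 15 minutes later. The section does not say who hands over the inhaler. No section says who holds the sequence list, or that collectors are kept from the list or the letter.

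**The concern.** The lettering hides what is in the inhaler. It does not hide the letter, and the letter is linked to ozone status through the printed sequences. The chamber, the separate operator and the sham operation conceal the generator, but they have no effect on an inference drawn from inhaler letters.

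Ozone is one of the two independent variables, and the section states that "Pre and post measures will be compared from the four conditions", which includes ozone versus room air. The outcome most open to influence is spirometry, because Measures/Instruments notes that an accurate reading depends on full inhalation and exhalation. That a collector who knew the exposure might coach effort differently is an assumption. FeNO is read by a monitor and blood pressure by an automated device, so both are little exposed. Symptoms are rated by participants, whose own blind is not shown to fail.

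**Working it through.** **Inputs.** Condition coding and sequences: Study Design. Order of events within a visit and visit numbering: Procedures. Number of participants, 24: Sample and Recruitment.

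**The plan's own figure.** The 24 is used here only as a multiplier. It can be reproduced with a paired t-test if 14% is read as a within-subject SD and alpha as two-sided (neither is stated). The SD of the difference is 14 × √2 = 19.8, the noncentrality is (12 / 19.8) × √24 = 2.97, and the power is 0.811.

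**Step 1: translate the sequences** (O = ozone, R = room air).

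| Sequence | Inhaler letters | Ozone status, exposures 1–4 |
|---|---|---|
| ABCD | A B A B | O O R R |
| BDAC | B B A A | O R O R |
| CABD | A A B B | R O O R |
| DCBA | B A B A | R R O O |

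**Step 2: list known and letters tracked at every exposure.** The first two letters are AB, BB, AA and BA, all different. At exposure 1 each letter is compatible with one ozone and one room-air start, so nothing is learned. From exposure 2 on, status is certain: 3 of 4 exposures per participant, or 12 of 16 sequence-exposures. With 24 completers there are 24 × 4 = 96 sessions, of which 24 × 3 = 72 are deducible, whatever the allocation.

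**Step 3: list known, less letter information.**
- Only the first letter remembered. A leaves ABCD or CABD, so exposure 2 is ozone and exposure 4 room air. B leaves BDAC or DCBA, so exposure 2 is room air and exposure 3 ozone. That is 24 × 2 = 48 of 96, whatever the allocation.
- Only that day's letter. Letter B at exposure 3 means ozone (CABD, DCBA); letter B at exposure 4 means room air (ABCD, CABD). That is 4 of 16, or 6 × 4 = 24 of 96 with 6 participants per sequence. The range is 0 (all BDAC) to 24 × 2 = 48 (all CABD).
- No letters. Down the four sequences, status is OORR, OROR, ROOO and RRRO at exposures 1 to 4. None is constant, so 0 of 16 are certain, but exposure 3 is ozone in 3 of 4 sequences and exposure 4 is room air in 3 of 4.

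**Step 4: which contrast is touched.** A condition escapes deduction only where it comes first, and each condition comes first once. So A, B, C and D are each deducible in 3 of 4 sequences. Under equal allocation, an additive effect of knowing the ozone status would fall alike on A and B and largely cancel from salbutamol versus placebo in ozone. It would not cancel from ozone versus room air.

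**Step 5: letters covered but devices distinguishable.** Seeing only same or different device gives pattern XYXY (ABCD, DCBA) or XXYY (BDAC, CABD). After XX, exposure 3 is always ozone and exposure 4 always room air. After XY, nothing is fixed. That is again 4 of 16: 24 of 96 with 6 per sequence, range 0 to 48 by allocation.

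**Step 6: would changing CABD to CADB close the route?** CADB gives letters AABB and status RORO. The first two letters still separate the sequences, so tracked letters again give 12 of 16, or 72 of 96.

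**The case against.** The strongest reply is that harm needs a chain of steps the documents do not state: collectors see the letters, know the list, track letters across visits, and then coach differently. This stands as a limit. The first two steps are plausible, since lettering by a non-collector makes most sense if collectors see lettered inhalers, and the list is printed in the protocol. Plausible is not shown, however. A reader might infer that staff are in fact unblinded; the documents support only that nothing prevents it.

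Second, the hypothesis concerns salbutamol versus placebo in ozone. This also stands. A reader might infer that the drug blind is broken too, but the letter order says nothing about which inhaler is placebo.

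Third, spirometry has some protection. It is done twice and the best attempt is used, participants practise beforehand, and a coaching effect that is equal before and after exercise drops out of the change. Only coaching that differs between the two would bias the comparison. These points lower the risk without removing it.

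Fourth, recoding labels may not be enough. Measures/Instruments describes a trainer inhaler for placebo and does not say that it looks like the salbutamol device. This is correct, and the fix has to cover it.

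**Conclusion.** The point holds as a gap in the blinding text, at minor to moderate priority. The enumeration is certain. That collectors see the letters and know the list is an assumption, and so is any influence on effort. Given both pieces of information, up to 72 of 96 sessions can be deduced before measurement, at exposures 2 to 4 (lab visits 3 to 5); none can at exposure 1. These are counts of sessions open to unmasking. A reader might take them as a measure of bias, but the documents give nothing from which a bias could be estimated. The exposure is confined mainly to spirometry in the ozone versus room air comparison.

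**What to change.** In the blinding text of Study Design, replace the letters that collectors see. Suggested wording:

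> Inhalers reach data collectors under a code unique to each participant and exposure visit, on devices that data collectors cannot tell apart. The person who labels the inhalers, who does not collect data, holds the key and tells the ozone operator only that visit's ozone status. Data collectors do not have access to the assigned sequence until data collection is complete.

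If the devices cannot be told apart, sessions deducible with certainty fall from up to 72 to 0, even for someone who has read the list. If same and different devices remain recognisable, the 24 of 96 from step 5 (range 0 to 48) remain, so a cover label alone should not be described as closing the route.

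Someone who knows the list would still have 3-to-1 odds at exposures 3 and 4 under equal allocation. That comes from a separate error: the printed set is not the Latin square that the section describes (condition B appears twice in third place and D twice in fourth). Using CADB as the third sequence would make those odds even, but it does not replace the recoding.

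If site practice already keeps the letters from collectors, a sentence saying so would largely settle the point.

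The cost is up to 24 × 4 = 96 coded labels and a check that the devices match. The labeller, who now has only a labelling task, would also hold the key and relay ozone status to the operator throughout the trial. Treatments, measurements and sample size do not change.

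### The printed treatment sequences are not the carryover-balanced Latin square the protocol describes; CABD is probably a misprint for CADB

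*Combined protocol and SAP*

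**What the plan says.** All references are to the combined protocol and SAP.

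Study Design defines A and B as ozone with inhaler A and inhaler B, and C and D as room air with inhaler A and inhaler B. Participants are randomised to one of four orders: "The four condition sequences will be ABCD, BDAC, CABD, DCBA". This is the only place where the orders are listed. Three statements about them follow:

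- "each condition appears only once in each sequence and only once at a particular spot within the four sequences"
- the list is "balanced with respect to first order carry over effects because each condition precedes every other condition only once"
- as an example, "condition D is first only once and is preceded by condition A, B, and C only once"

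On the comparison, the same section says: "Pre and post measures will be compared from the four conditions". No analysis model is set out and no period term is named. The sample-size paragraph mentions F-tests from an analysis of variance, and arrives at 24 subjects from a 12% difference in FEV1, an SD of 14%, power 0.8 and alpha 0.05.

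Procedures adds: "All visits will be separated by 48 hours to prevent carryover effects from previous exposure to ozone or salbutamol". The reason it gives is: "This 48-hour duration was chosen because it is longer than five half-lives of salbutamol medication".

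**The concern.** The stated balance is a property of the design that can be checked by counting, and the printed list does not have it. A randomisation schedule built from this sentence would lack the protection the protocol says it has, and a report repeating the claim would describe a design that was not run.

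The contrast that bears on the Objective is A-minus-B, the two inhalers compared in ozone. Which inhaler holds salbutamol is blinded, so the direction of any shift relative to salbutamol is unknown here. As printed, A follows an ozone visit in one sequence and B in two. Anything left over from a previous ozone visit therefore falls unequally on the two arms of the contrast. The reason given for the 48-hour gap concerns salbutamol only, so for ozone the ordering is the design's other safeguard. The unequal visit positions also let a drift over visits enter the contrast if period is not in the model.

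**Working it through.** **1. The stated properties, by count**

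| | Period 1 | Period 2 | Period 3 | Period 4 |
|---|---|---|---|---|
| Sequence 1 | A | B | C | D |
| Sequence 2 | B | D | A | C |
| Sequence 3 | C | A | B | D |
| Sequence 4 | D | C | B | A |

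- Each condition once per sequence: true.
- Each condition once per period: true for periods 1 and 2. Period 3 is C, A, B, B and period 4 is D, C, D, A, so false.
- Each ordered adjacent pair once: AB 2, BD 2, AD 0, DB 0, the other eight 1 each, so false.
- D first once: true. D preceded once each by A, B and C: it is preceded by B twice, C once and A never, so false.

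Replacing each sequence in turn by all 24 orderings, only CABD to CADB gives a Latin square. That square also has all 12 ordered pairs exactly once.

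**2. Shifts if CABD is used**

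Assumptions: 24 participants, 6 per sequence, all complete. R is the shift in the analysed outcome at a visit that follows an ozone visit, equal after A and after B.

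Without a period term, each contrast is a difference of condition means. The share of visits that follow ozone is:

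| | A | B | C | D |
|---|---|---|---|---|
| Printed list | 1/4 | 2/4 | 2/4 | 2/4 |
| With CADB | 1/4 | 1/4 | 2/4 | 2/4 |

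- A-minus-B, printed: (0.25 - 0.50)R = -0.25R. With CADB: 0.
- Interaction (A-B)-(C-D), printed: -0.25R - 0 = -0.25R. With CADB: 0.
- Ozone minus air, printed: (0.375 - 0.50)R = -0.125R. With CADB: (0.25 - 0.50)R = -0.25R.

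With a period term, fit participant, period and condition by least squares. With design matrix X, contrast vector L and previous-ozone indicator c, the shift is L(X'X)⁻¹X'c times R. Printed list: A-minus-B -0.33R, interaction -0.42R, ozone minus air -0.04R. With CADB: 0, 0 and -0.25R.

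**3. Drift of d per visit, no period term**

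Mean visit position, printed: A (1+3+2+4)/4 = 2.5; B (2+1+3+3)/4 = 2.25; C (3+4+1+2)/4 = 2.5; D (4+2+4+1)/4 = 2.75. A-minus-B shifts by 0.25d, and the interaction by 0.25d - (-0.25d) = 0.50d. With CADB every mean is 2.5 and both shifts are 0.

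**4. Precision** (variances in units of within-person variance, L(X'X)⁻¹L')

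| | No period term, either list | Period term, CABD | Period term, CADB |
|---|---|---|---|
| A-minus-B | 2/24 = 0.0833 | 0.0903 | 0.0833 |
| Interaction | 4/24 = 0.1667 | 0.1944 | 0.1667 |

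With period fitted the ratios are 0.0903/0.0833 = 1.08 and 0.1944/0.1667 = 1.17. Without it there is no difference between the lists.

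The plan's 24 subjects reproduce if 14% is read as the within-person SD: SD of a difference 14 × √2 = 19.8, paired two-sided t test at 0.05, n = 24, power 0.811. On that reading, in the four-condition model with period (66 df):

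- CABD: SE = 14 × √0.0903 = 4.21; 12/4.21 = 2.85; power 0.80.
- CADB: SE = 14 × √0.0833 = 4.04; 12/4.04 = 2.97; power 0.83.

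**5. Scale of R**

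The documents give no value for R. Taking |R| = 0, 0.25 or 0.5 within-person SD as an assumption, with CABD and a period term, A-minus-B moves by 0, 0.08 or 0.17 SD against an SE of 0.30 SD (√0.0903). Its false-positive rate is 5.0%, 5.9% or 8.5%.

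**6. Unequal carryover**

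If only A leaves a residual, CADB still shifts A-minus-B and the interaction by -0.25 each per unit of residual. The printed list with a period term gives -0.58 and -0.92.

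**The case against.** The strongest reply is that this is a typing error. One two-letter swap makes every sentence in the paragraph true, which is hard to explain if the authors did not have the correct square in front of them. That stands, and a reader should not infer that participants were allocated to CABD. Equally, nothing in the documents shows that they were not.

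Second, harm needs more than CABD. It also needs an ozone residual, an unadjusted drift or, for precision, a period term the plan does not name. A residual that is stable within a visit cancels from pre-to-post change, the comparison the plan appears to describe. This also stands, with a limit: it does not cover post-exercise levels analysed as such, or a residual that alters the response to the next exposure.

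Third, CADB is not a complete safeguard. Its zeros need equal carryover under both inhalers, yet the Hypothesis expects more inflammation with salbutamol, so unequal carryover is plausible. They also need equal allocation, and the plan does not mention blocking. With 8, 6, 4 and 6 participants in the four sequences, CADB with period shifts the interaction by -0.16R. CADB also leaves a larger equal-residual shift in ozone-versus-air than the printed list does. All of this is correct: CADB reduces the problem for the inhaler contrasts without abolishing it.

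Finally, all contrasts remain estimable under the printed list.

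**Conclusion.** The printed list contradicts the protocol's own description. Uniformity within sequences and D coming first once hold; uniformity within periods, pair balance and the worked example for D do not. This is certain, because it is a count on the only list given. That CABD is a misprint for CADB is probable but is an inference.

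If CABD was used, the consequence is moderate and conditional. An equal prior-ozone residual shifts A-minus-B by a quarter to a third of its size, and the interaction by 0.25 to 0.42 of it, depending on whether period is fitted. Without period, drift also enters. With period, there is an 8% or 17% variance penalty. These figures rest on six complete participants per sequence, and the power figures also on reading 14% as the within-person SD.

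Two stronger readings are not supported. One is that the trial loses power regardless of how it is analysed: without a period term the variances are identical under both lists. The other is that 48 hours is too short for ozone: the documents give no ozone-specific reason for the interval, but they do not show a residual either, and R may be zero.

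**What to change.** 1. Replace CABD with CADB in Study Design and confirm which list was used for randomisation. Before randomisation starts this costs two letters and no data. If CADB was used all along, only the text needs correcting.

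2. Include period in the analysis model. With CADB this leaves the variances in the working unchanged.

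3. If CABD was used, report it, withdraw the balance claim, and fit period plus one term for ozone at the previous visit. A-minus-B variance rises from 0.0903 to 0.0982 (about 9%) and power goes from 0.80 to about 0.77. The single term assumes equal carryover under both inhalers. Separate terms by inhaler raise the variance to 0.1372 (power 0.63), so keep them for sensitivity analysis.

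4. With CADB the previous-visit-ozone term is optional. It removes the -0.25R shift in ozone-versus-air, leaves A-minus-B variance at 0.0833, and raises ozone-versus-air variance from 0.0417 to 0.0458 (about 10%).
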